PROTOCOL

A Pilot Study of Single-Agent Ibrutinib in Relapsed or Refractory Transformed Indolent B-Cell Non-Hodgkin Lymphoma

Trial of the Fred Hutchinson Cancer Center (FHCC) and the University of Washington (UW)

Supported in part by Janssen Scientific Affairs, LLC

**Protocol Version Date: 07/18/2022
Previous Version Date: 04/23/2020**

SPONSOR-INVESTIGATOR:

[name]
Professor, UW
Member, FHCC
Fred Hutchinson Cancer Center
[name]
[name]
[contact]

Lead Sub-Investigator:
[name]
Acting Instructor, UW
Fred Hutchinson Cancer Center
[name]
[name]
[contact]

PROTOCOL ACTIVITY

Accrual Activated:

Protocol Revision Record:

Original Version: Version 3, Dated 06/17/2014

Amendment #1: Version 4, Dated 10/23/2015

Amendment #2: Version 5, Dated 02/27/2019

Amendment #3: Version 6.0, Dated 04/23/2020

Amendment #4: Version 7.0, Dated 07/18/2022

SCHEMA

Registration

Ibrutinib 560 mg PO taken daily continuously on a 21-day cycle

Continued until intolerance, progressive disease, or the discretion of patient / clinician

Stop ibrutinib

Routine clinical follow-up for up to 5 years

TABLE OF CONTENTS:

1.0	Objectives	5
2.0	Background and Rationale	5
3.0	Drug Information	6
4.0	Staging Criteria	9
5.0	Eligibility Criteria	9
6.0	Registration	12
7.0	Treatment Plan	12
8.0	Dosage Modifications	13
9.0	Study Calendar	16
10.0	Criteria for Evaluation and Endpoint Definitions	17
11.0	Statistical Considerations	18
12.0	Study Monitoring and Reporting Procedures	19
13.0	Elements of Informed Consent	26
14.0	References	27

1.0 OBJECTIVES

1.1 Primary objectives

- 1.1.1 Perform a preliminary assessment of the efficacy of single-agent ibrutinib, based on overall response rate, in subjects with relapsed or refractory transformed indolent B-cell non-Hodgkin lymphoma (R/R TIL).

1.2 Secondary objectives

- 1.2.1 To determine the tolerability of chronic ibrutinib therapy in this patient population.
- 1.2.2 To determine the disease control rate of this regimen.
- 1.2.3 Evaluate the complete response rate, overall survival, and progression-free survival to single-agent ibrutinib in this patient population.
- 1.2.4 Determine response rate relative to the underlying B-cell histology.

2.0 BACKGROUND

2.1 Transformed indolent B-cell non-Hodgkin lymphoma

Indolent B-cell non-Hodgkin lymphomas are comprised of several histologic subtypes, including follicular lymphoma (FL), chronic lymphocytic leukemia (CLL), and marginal zone lymphoma (MZL). As a disease class, it is incurable short of allogeneic transplantation and shows a variable natural history. The course is typically slowly progressive at the outset and responsive to cytotoxic and immunologic therapies. Most patients eventually relapse with a disease phenotype that is increasingly resistant to treatment, with shorter intervals of response, over time [1, 2]. At a rate of approximately 3% per year, indolent B-cell non-Hodgkin lymphomas transform into more aggressive malignancies that share a clonal relationship with the original disease [3].

Transformed indolent B-cell non-Hodgkin lymphoma (TIL) is classically diagnosed with histologic demonstration of an increased proportion, compared with the original specimen, of large neoplastic cells. Though typically transformation is to DLBCL, other subtypes, including to unclassifiable B cell lymphoma (BCLU), lymphoblastic lymphoma, and acute lymphocytic leukemia (ALL) also occur [4]. Clinically, transformation is often reflected by a rapid rise in LDH, discordant localized nodal growth, or new B-type symptoms [4, 5]. Treatment paradigms for TIL are dictated by prior therapies and patient characteristics. High dose therapy (HDT) followed by consolidation with autologous stem cell transplantation (ASCT) appears to benefit select patients, with estimates of 5-year overall survival ranging from 37 – 65% [6-9], but this procedure is generally limited to a subset of patients with chemotherapy-sensitive disease and in good physical condition. Involved-field radiotherapy is beneficial in the subset of patients with early stage disease. For cases of relapsed or refractory TIL (R/R TIL), few therapeutic strategies of proven benefit are available. Radioimmunotherapy has activity in a subset of patients with R/R TIL and is approved for this indication; however its role is not yet clearly defined [10].

2.2 Ibrutinib in lymphoma

The B-cell antigen receptor (BCR) transmits proliferation signals during normal B cell development and its signaling activity has been shown to play a role in a variety of B cell malignancies, including follicular lymphoma [11, 12]. The Bruton's tyrosine kinase (BTK) is an essential component of the BCR pathway; its absence results in the arrest of normal peripheral B cell maturation and, consequently, low levels of circulating immunoglobulin [13, 14]. Ibrutinib (PCI-32765) is a small molecule that selectively and covalently inhibits BTK and has shown activity in several B cell malignancies, including previously treated mantle cell lymphoma and chronic lymphocytic leukemia, for which its administration is FDA approved [15]. Early data also suggest a benefit in FL, with an overall response rate in 6 of 11 patients treated on PCYC-04753, and in DLBCL [16]. Ibrutinib is not currently FDA approved for these diseases nor for RR/TIL. Ibrutinib has been shown to modulate B-cell chemotaxis and migration and promote apoptosis [17]. It is taken orally and, to date, has demonstrated a very good safety profile with reported adverse events mostly grade 1 and 2 in severity and typically self-limited in duration [15, 18].

2.3 Summary

R/R TIL presents a great therapeutic challenge and requires novel strategies. Ibrutinib has shown significant promise in treating several B-cell malignancies, and its oral administration and favorable toxicity profile make it an especially attractive candidate in advanced, previously treated disease. We hypothesize that its use will achieve significant and durable responses in a subset of patients with R/R TIL, thus adding to the limited selection of therapeutic options for this disease.

3.0 DRUG INFORMATION

3.1 General Information

Ibrutinib is an orally-administered, covalently-binding small molecule inhibitor of Bruton's tyrosine kinase, currently being co-developed by Pharmacyclics, Inc. and Janssen Scientific Affairs, LLC in B-cell malignancies.

3.2 Administration

Each capsule contains 140 mg of ibrutinib. The capsules are to be taken once daily around the same time each day. They should be swallowed whole and should not be opened, broken, or chewed. If a dose of ibrutinib is not taken at the scheduled time, it can be taken as soon as possible on the same day with a return to the normal schedule the following day. Extra capsules of ibrutinib should not be taken to make up for the missed dose.

3.3 Toxicity

3.3.1 Adverse events

Refer to the current FDA-approved package insert or the *Physician Desk Reference*.

The most common adverse reactions ($\geq 20\%$) in patients with MCL were thrombocytopenia, diarrhea, neutropenia, anemia, fatigue, musculoskeletal

pain, peripheral edema, upper respiratory tract infection, nausea, bruising, dyspnea, constipation, rash, abdominal pain, vomiting and decreased appetite.

The most common adverse reactions ($\geq 20\%$) in patients with CLL were thrombocytopenia, diarrhea, bruising, neutropenia, anemia, upper respiratory tract infection, fatigue, musculoskeletal pain, rash, pyrexia, constipation, peripheral edema, arthralgia, nausea, stomatitis, sinusitis, and dizziness.

3.3.2 Hemorrhage

Five percent of patients with MCL and 6% of patients with CLL had Grade 3 or higher bleeding events (subdural hematoma, ecchymoses, gastrointestinal bleeding, and hematuria). Overall, 4 bleeding events including bruising of any grade occurred in 48% of patients with MCL treated with 560 mg daily and 63% of patients with CLL treated at 420 mg daily. The mechanism for the bleeding events is not well understood. Ibrutinib may increase the risk of hemorrhage in patients receiving antiplatelet or anticoagulant therapies. Consider the benefit-risk of withholding ibrutinib for at least 3 to 7 days pre and postsurgery depending upon the type of surgery and the risk of bleeding. Subjects in the current study will be monitored closely for hemorrhagic adverse events. Guidance on use of antiplatelet agents and anticoagulants is provided in Section 3.4.3.

3.3.3 Other Malignancies

Other malignancies have occurred in 5% of patients with MCL and 10% of patients with CLL who have been treated with ibrutinib. Four percent of patients with MCL, had skin cancers and 1% had other carcinomas. Eight percent of patients with CLL had skin cancers and 2% had other carcinomas. It is not clear whether or not these events are attributable to ibrutinib.

3.4 Drug Interactions

3.4.1 Metabolism

Ibrutinib is metabolized primarily by CYP3A. In healthy volunteers, co-administration of ketoconazole, a strong CYP3A inhibitor, increased Cmax and AUC of ibrutinib by 29- and 24-fold, respectively. The highest ibrutinib dose evaluated in clinical trials was 12.5 mg/kg (actual doses of 840 – 1400 mg) given for 28 days with single dose AUC values of $1445 \pm 869 \text{ ng} \cdot \text{hr}/\text{mL}$ which is approximately 50% greater than steady state exposures seen at the highest indicated dose (560 mg). Avoid concomitant administration of ibrutinib with strong or moderate inhibitors of CYP3A. For strong CYP3A inhibitors used short-term (e.g., antifungals and antibiotics for 7 days or less, e.g., ketoconazole, itraconazole, voriconazole, posaconazole, clarithromycin, telithromycin) consider interrupting ibrutinib therapy during the duration of inhibitor use. Avoid strong CYP3A inhibitors that are needed chronically. If a moderate CYP3A inhibitor must be used, reduce the ibrutinib dose. Patients taking concomitant strong or moderate CYP3A4 inhibitors should be monitored more closely for signs of ibrutinib toxicity. Avoid grapefruit and Seville oranges during ibrutinib treatment, as these contain moderate inhibitors of CYP3A.

Administration of ibrutinib with strong inducers of CYP3A decrease ibrutinib plasma concentrations by approximately 10-fold. Avoid concomitant use of strong CYP3A inducers (e.g., carbamazepine, rifampin, phenytoin and St. John's Wort). Consider alternative agents with less CYP3A induction. Appendix C outlines some of the inhibitors and inducers of CYP3A.

3.4.3 Concomitant Use of Ibrutinib and Antiplatelet Agents and Anticoagulants

There have been reports of hemorrhagic events in subjects treated with ibrutinib, both with and without thrombocytopenia. These include minor hemorrhagic events such as contusion, epistaxis and petechiae; and major hemorrhagic events including gastrointestinal bleeding, intracranial hemorrhage, and hematuria. Also, patients with congenital bleeding diathesis have not been studied. Warfarin or vitamin K antagonists should not be administered concomitantly with ibrutinib. Supplements such as fish oil and vitamin E preparations should be avoided. Ibrutinib should be withheld at least 3 to 7 days pre- and post-surgery depending upon the type of surgery and the risk of bleeding (see Section 5.3). Ibrutinib should be used with caution in subjects requiring other anticoagulants or medications that inhibit platelet function. It is possible that treatment with ibrutinib may increase the risk of bruising or bleeding, particularly in subjects receiving antiplatelet agents or anticoagulants. Subjects receiving antiplatelet agents in conjunction with ibrutinib should be observed closely for any signs of bleeding and ibrutinib should be held in the event of major bleeding events defined as adverse event of special interest (Section 12).

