5.2 Exclusion Criteria

5.2.1 Known history of human immunodeficiency virus (HIV) or active Hepatitis C Virus or active Hepatitis B Virus infection or any uncontrolled active systemic infection.

5.2.2 Major surgery or a wound that has not fully healed within 4 weeks of initiation of therapy.

5.2.3 Known central nervous system lymphoma.

- 5.2.4 History of stroke or intracranial hemorrhage within 6 months of screening.
- 5.2.5 Requires anticoagulation with warfarin or equivalent vitamin K antagonists (e.g., phenprocoumon).
- 5.2.6 Requires chronic treatment with strong CYP3A inhibitors.
- 5.2.7 Clinically significant cardiovascular disease such as uncontrolled or symptomatic arrhythmias, congestive heart failure, or myocardial infarction within 6 months of screening, or any Class 3 (moderate) or Class 4 (severe) cardiac disease as defined by the New York Heart Association Functional Classification.
- 5.2.8 Vaccinated with live, attenuated vaccines within 4 weeks of initiation of therapy.
- 5.2.9 Any life-threatening illness, medical condition, or organ system dysfunction which, in the investigator's opinion, could compromise the subject's safety, interfere with the absorption or metabolism of ibrutinib capsules, or put the study outcomes at undue risk.
- 5.2.10 Patients with other prior malignancies except for adequately treated basal cell carcinoma, squamous cell carcinoma of the skin, breast or cervical cancer *in situ*, or other cancer from which the patient has been disease-free for 5 years or greater, unless approved by the protocol Sponsor-Investigator / Lead-Sub-Investigator.
- 5.2.11 Patients that previously were treated with ibrutinib for > 7 days.
- 5.2.12 Previous chemotherapy, immunotherapy, biologically targeted therapy, other investigational agent, or radiation therapy within 3 weeks of initiation of ibrutinib therapy or radio-immunotherapy within 12 weeks of initiation of ibrutinib therapy.
- 5.2.13 Prior allogeneic transplant with GVHD requiring immunosuppressive therapy.

- 5.3 Restrictions: The following guidance should be considered during the perioperative period for subjects who require surgical intervention (including oral surgery) or an invasive procedure while receiving ibrutinib:

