8.0 DOSAGE MODIFICATIONS

8.1 Dose Modification and Dose Delay

Treatment with ibrutinib should be held for any of the toxicities listed below:

- 8.1.1 Grade 4 neutropenia (ANC < 500/mm³)
- 8.1.2 Grade 3 thrombocytopenia (platelets < 50,000/mm³) in the presence of significant bleeding (\geq Grade 2 bleeding)
- 8.1.3 Grade 4 thrombocytopenia (platelets < 25,000/mm³)
- 8.1.4 Grade 3 or Grade 4 nausea, vomiting or diarrhea (if persistent despite optimal antiemetic or antidiarrheal therapy) or any other Grade 4 or unmanageable Grade 3 drug-related toxicities.

The following actions should be taken for drug-related toxicities:

Occurrence of the Same Adverse Event	Action
First	Hold ibrutinib until recovery to Grade ≤ 1 or baseline; may restart at original dose level
Second	Hold ibrutinib until recovery to Grade ≤ 1 or baseline; restart at 1 dose level lower (420 mg daily)
Third	Hold ibrutinib until recovery to Grade ≤ 1 or baseline; restart at 1 dose level lower (280 mg daily)
Fourth	Discontinue ibrutinib

Ibrutinib may be held for a maximum of 21 consecutive days. Ibrutinib should be discontinued if the treatment cannot be resumed within 21 days. Once the ibrutinib dose is reduced because of toxicity, it cannot be re-escalated. No dose escalation of ibrutinib (above 560 mg) is allowed in this study. Refer to section 3.4 for subjects requiring the initiation of anticoagulants while receiving study

drug and for instructions on dose modification or temporary hold during concomitant administration of CYP3A inhibitors or inducers. Refer to section 5.3 for guidance on dose delays during the perioperative period for subjects who require surgical intervention or an invasive procedure while receiving study drug.

If there is a rapid increase in disease burden leading to an "apparent" response of PD after the study drug has been held for at least 7 consecutive days, an assessment response of tumor flare may be assigned instead of PD. Should this occur the patient may remain on study drug if they otherwise meet criteria to continue until the next restaging exam unless there is ongoing evidence of progressive disease before that time despite ongoing treatment. If there is further documented PD on or before the next restaging evaluation the patient will be considered to have PD and the date of PD will be assigned to the initial date tumor flare.

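### Sections 8.1 and 8.2 set different doses after the same severe toxicity and neither is said to govern; separately, the major-bleed hold in 3.4.3 does not clearly reach subjects who take no antiplatelet agent

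*Combined protocol and SAP*

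**What the plan says.** **Dose after a severe toxicity.** Section 8.1 lists when ibrutinib is held: Grade 4 neutropenia, Grade 4 thrombocytopenia, Grade 3 thrombocytopenia "in the presence of significant bleeding" (Grade 2 or higher), persistent severe gastrointestinal toxicity, and "any other Grade 4 or unmanageable Grade 3 drug-related toxicities". An action table then sets the dose by occurrence of the same event. Section 8.1 also forbids re-escalation and caps a hold at 21 days.

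Section 8.2 follows with Table 1, which sets its own doses by occurrence for other Grade 3 or 4 non-hematological toxicities and for Grade 4 hematological ones. It calls its recommendations updated but does not mention the 8.1 table. The column for a 560 mg start is headed MCL and MZL; transformed lymphoma appears in neither column.

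**Hold for bleeding.** Section 3.3.2 states: "Guidance on use of antiplatelet agents and anticoagulants is provided in Section 3.4.3". Section 3.4.3 then says "Ibrutinib should be used with caution in subjects requiring other anticoagulants or medications that inhibit platelet function" and notes that bleeding risk may rise, "particularly in subjects receiving antiplatelet agents or anticoagulants". Its last sentence begins "Subjects receiving antiplatelet agents in conjunction with ibrutinib should be observed closely for any signs of bleeding" and continues that "ibrutinib should be held in the event of major bleeding events defined as adverse event of special interest (Section 12". Exclusion 5.2.5 reads "Requires anticoagulation with warfarin or equivalent vitamin K antagonists", so other anticoagulants remain permitted. Section 12.2.3 counts a bleed as major if it is Grade 3 or higher, or if it leads to vision loss, transfusion of two or more red-cell units, or new or longer hospitalization. It also captures intracranial hemorrhage of any grade. It sets 24-hour reporting for these events, not a hold.

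**The concern.** The main issue is that two schedules, both in the current text, cover the same Grade 4 or unmanageable Grade 3 drug-related events, and they differ. Two physicians can each follow the protocol and give different doses; at a third event one continues ibrutinib and the other stops it. This is not specific to bleeding. Tolerability is a secondary objective (1.2.1), and in about 20 patients inconsistent dosing after toxicity would blur it.

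The secondary issue is the hold itself. The only hold tied to the Section 12 bleed definitions sits in a sentence whose subject is antiplatelet users, although 3.4.3 has just named anticoagulant users as a raised-risk group and 3.3.2 has promised guidance for both. The events left unclear are ones the protocol singles out for enhanced reporting.

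**Working it through.** **1. The two schedules side by side** (Grade 4 or unmanageable Grade 3 drug-related toxicity, 560 mg start, general row of Table 1)

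| Occurrence | Section 8.1 | Section 8.2, Table 1 |
|---|---|---|
| First | may restart at 560 mg | 420 mg |
| Second | one level lower, stated as 420 mg | 280 mg |
| Third | 280 mg | discontinue |
| Fourth | discontinue | already off drug |

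- First event: 8.1 is permissive, so 420 mg satisfies both schedules.
- Second event: the stated doses differ by 420 − 280 = 140 mg. The split is clear mainly for a patient who restarted at 560 mg. For one who restarted at 420 mg, one level lower is 280 mg, which agrees with Table 1 but not with the dose printed in 8.1.
- Third event: the instructions cannot be reconciled.

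**2. How often, for severe bleeds**

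Inputs: 5% with Grade 3 or higher bleeding (section 3.3.2, MCL patients), assumed to carry over; 20 patients (section 11.3), or 40 with the expansion in 11.4. The share who bleed severely again after restart is not in the documents; 10% to 30% at each step is an assumption. The expected number is n × p, and the chance of at least one patient is 1 − (1 − p)^n.

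- Second event: p = 0.05 × 0.10 = 0.005 to 0.05 × 0.30 = 0.015. With n = 20, expected 0.1 to 0.3; chance 1 − 0.995^20 = 10% to 1 − 0.985^20 = 26%. With n = 40, expected 0.2 to 0.6; chance 18% to 45%.
- Third event: p = 0.05 × 0.10 × 0.10 = 0.0005 to 0.05 × 0.30 × 0.30 = 0.0045. With n = 20, expected 0.01 to 0.09; chance 1 − 0.9995^20 = 1% to 1 − 0.9955^20 = 9%. With n = 40, expected 0.02 to 0.18; chance 2% to 17%.

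Given these assumptions, these are upper figures for bleeds, because manageable Grade 3 bleeds fall outside 8.1.4. They do not count other toxicities to which both schedules apply.

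**3. Which rule holds drug for which bleed** (subject not on an antiplatelet agent, platelets 50,000/mm³ or above)

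- Grade 3 or 4 bleed: interrupted by Table 1, and by 8.1.4 if Grade 4 or unmanageable.
- Bleed below Grade 3 that is major under 12.2.3 item 1: no explicit hold unless the 3.4.3 clause is read as general.
- Grade 1-2 intracranial hemorrhage: the same.
- With thrombocytopenia the picture changes: 8.1.2 holds for Grade 2 or higher bleeding with platelets below 50,000/mm³, and 8.1.3 holds below 25,000/mm³ regardless of bleeding.
- Sections 7.4.2 and 7.4.3 concern removal from treatment; neither sets a hold.

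**The case against.** **On the dose schedules.** Section 8.2 is directive and calls itself updated, so a reader may fairly suppose that it was meant to replace 8.1. That is probably the intent, but 8.1 stands in full and no sentence sets precedence. It is also fair that a physician who follows Table 1 at the first event meets little conflict at the second. A reader might infer that the choice between continuing and stopping arises after any repeat severe bleed, and attach the 0.1 to 0.3 figure to it. The schedules do not support that: the choice arises only at the third occurrence.

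**On the hold.** The clause in 3.4.3 has its own grammatical subject. The section is titled for both drug classes and opens with bleeds in ibrutinib subjects generally, and 8.1 sends readers to 3.4 when a subject starts an anticoagulant. A general reading is therefore reasonable. A reader might infer that subjects not on antiplatelet agents have no hold for bleeding at all. That goes too far, since Table 1 interrupts Grade 3 and 4 bleeds in everyone and 8.1.2 and 8.1.3 act when platelets are low. A reader might also infer that a Grade 1 intracranial bleed, already within the 8.1 recovery limit, may restart at once at 560 mg. That is hypothetical, because neither schedule clearly applies to such an event.

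**Safeguards.** Section 3.3.2 requires close monitoring of all subjects for bleeding, 7.1 names contacts for dose questions, and 12.4 has possibly related events of interest reported promptly to the sponsor-investigator. A bleed needing hospitalization is a serious event that qualifies for removal consideration under 7.4.2. A physician would probably hold drug anyway. All this lowers the weight of the second point; none of it supplies the missing sentence.

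**Conclusion.** The main point holds. For Grade 4 or unmanageable Grade 3 drug-related toxicity, 8.1 and Table 1 differ and nothing settles which applies. The conflict is permissive at the first event, depends mainly on the restart dose at the second, and is direct at the third. For severe bleeds in 20 patients, about 0.1 to 0.3 reach a second event and 0.01 to 0.09 a third (1% to 9% chance of at least one). This rests on the 5% MCL rate carrying over, on the assumed 10% to 30% repeat share, and on the 560 mg column being the one intended, which the study dose suggests but the column heading does not say.

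The second point holds at lower severity, as unclear wording rather than a proven absence of a hold. Its frequency cannot be estimated: the documents give no rate of major or intracranial bleeds below Grade 3 and no share of subjects on antiplatelet agents. It may be low, since 3.3.2 lists subdural hematoma among Grade 3 or higher events, which Table 1 already interrupts.

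**What to change.** 1. In 8.2, state that the 560 mg column of Table 1 applies to this study's transformed lymphoma patients and replaces the 8.1 occurrence table wherever both apply.
2. In 8.1, add for all subjects, whatever their concomitant drugs: *Hold ibrutinib for any major hemorrhage per 12.2.3 item 1 and any intracranial hemorrhage of any grade; resume only after the bleed has resolved or stabilized and the sponsor-investigator has reviewed benefit-risk.*
3. Edit the last sentence of 3.4.3 so that the hold applies to all subjects and points to the new 8.1 entry.

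The cost is one sentence in 8.2, one line in 8.1 and one edited sentence in 3.4.3. In practice there would be a few more holds. Section 8.1 anticipates tumor flare after 7 or more days off drug, and 8.1 and 7.4.4 end treatment when a hold passes 21 days, so a patient could lose treatment. Making Table 1 govern also brings earlier reduction and stopping after repeat severe events, with no re-escalation. The dose after a bleed below Grade 3 should stay with the benefit-risk review rather than be reduced automatically.
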